6.5.2 Treatment assignment or randomization

Eligible patients will be assigned to one of the 2 treatment arms ([Section 4.1](#) and [Section 6.1](#)) in a ratio of 2:1 (osilodrostat: placebo respectively).

Randomization will be stratified at Day 1 according to history of pituitary irradiation (yes/no).

The randomization numbers will be generated using the following procedure to ensure that treatment assignment is unbiased and concealed from patients and investigator staff. A patient randomization list will be produced by the Interactive Response Technology (IRT) provider using a validated system that automates the random assignment of subject number to randomization numbers. These randomization numbers are linked to the different treatment arms, which in turn are linked to medication numbers. A separate medication randomization list will be produced by or under the responsibility of Novartis Drug Supply Management using a validated system that automates the random assignment of medication numbers to medication packs containing each of the study drugs.

Prior to dosing, all patients who fulfill all inclusion/exclusion criteria will be randomized via IRT to one of the 2 treatment arms. The investigator or his/her delegate will call or log on to the IRT and confirm that the patient fulfills all the inclusion/exclusion criteria. The IRT will

assign a randomization number to the patient, which will be used to link the patient to a treatment arm and will specify a unique medication number for the first package of study drug to be dispensed to the patient. The randomization number will not be communicated to the caller.

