10.5.2 Other secondary efficacy objectives

10.5.2.1 Assess the overall response rate at Week 12, Week 36, and Week 48

Proportion of overall responders (enrolled patients with mUFC \leq ULN or have at least 50% reduction in mUFC from baseline and $>$ ULN) at Week 12, Week 36 and Week 48 will be summarized using point estimates and Clopper-Pearson 95% CIs by treatment arms and for overall patients. For the osilodrostat arm, denominator will be the number of patient randomized to osilodrostat; whereas for placebo arm, denominator will be number of randomized patients switched to osilodrostat.

10.5.2.2 Assess the change in mUFC during the Core and optional Extension periods of the study

For the actual and percentage change in mUFC from baseline, descriptive summaries will be provided for every visit in Core and optional extension phase at which UFC is collected. 95% CIs for the percentage change from baseline will also be provided by treatment arms and for overall patients.

10.5.2.3 Compare the time-to-first control of mUFC during the placebo-controlled period between patients randomized to osilodrostat and placebo

Time-to-first control of mUFC during the placebo control period will be analyzed using Kaplan-Meier plots and the logrank test. Time-to-first control of mUFC is defined as the time (in days) from randomization to the time of the first post-baseline mUFC collection that was \leq ULN (based on central lab result) before discontinuation or completion of placebo-controlled period, whichever is earlier.

10.5.2.4 Assess the time-to-escape during treatment of osilodrostat up to Week 48

For patients who attained normal mUFC (\leq ULN), time-to-escape will be analyzed using Kaplan-Meier plots. This will be performed by randomized treatment assignment and for the overall trial population. Time-to-escape is defined as the time (in weeks) from the first collection of post-baseline normal mUFC (\leq ULN) to the first mUFC $>$ 1.3 x ULN on 2 consecutive visits on the highest tolerated dose of osilodrostat and not related to a dose interruption or dose reduction due to safety reasons. Time-to-escape will not be assessed for patients during the first 26 weeks.

Patients that have dose interruption or dose reduction for safety reasons will be censored at the time of the first dose interruption.

10.5.2.5 Assess the change from baseline in cardiovascular and metabolic related parameters associated with Cushing's disease during the core period of the study

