2.1 Data analysis general information

The primary analysis will be performed when all enrolled patients have completed the Core phase of study (Period 1 and 2) or have prematurely withdrawn from the study prior to the end of the Core phase at Week 48. The results and outcomes of this analysis will be presented in a CSR. After the Core study phase, patients receiving clinical benefit from osilodrostat treatment have the option to enter a 48-week extension phase. The additional data collected in the extension phase, will be further summarized in a final study report once these patients completed the study. There is no interim analysis planned for this study.

Novartis or designated CRO will analyze all data using the SAS System for data analysis V9.4 or higher. Any data analyses carried out independently by an investigator should be submitted to Novartis and approved before publication or presentation.

The data from all centers participating in the trial will be combined, so that an adequate number of patients will be available for analysis. The statistical analysis methods described in this section will focus on the analysis of the data in the Core study. Similar methods will be applied to the analyses in the extension phase as appropriate.

All data with an assessment date or event start date (e.g. vital sign assessment date or start date of an adverse event) prior to or on the cut-off date will be included in the analysis. Any data collected beyond the cut-off date will not be included in the analysis and will not be used for any derivations.

The randomization will be stratified by history of pituitary irradiation. To take stratification into account, the primary efficacy endpoint will be analyzed using Cochran-Mantel-Haenszel (CMH) exact test.

Categorical data or qualitative characteristics of a subject (e.g., gender, race, subject disposition, etc.) will be summarized by frequency count (number of subjects) and percentages. Percentages will be calculated using the number of subjects in the relevant population or subgroup as the denominator.

Continuous data (e.g., age, body weight, etc.) will be summarized by appropriate descriptive statistics (mean, standard deviation, median, minimum, and maximum).

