2.2 Analysis sets

2.2.1 Full Analysis Set

The Full Analysis Set (FAS) comprises all randomized patients who have received at least one dose of study drug (osilodrostat or placebo). According to the intent-to-treat (ITT) principle, patients will be analyzed according to the treatment and stratum they have been assigned to during the randomization. This is the default analysis set for efficacy. The randomization is stratified by history of pituitary irradiation yes/no.

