2.5.2 Statistical hypothesis, model, and method of analysis

For the primary objective, the statistical null hypothesis states that the complete response rates at the end of the 12-week placebo-controlled period (i.e., at Week 12) are the same between the two randomized arms. To test this hypothesis, a Cochran–Mantel–Haenszel (CMH) exact test stratified by the history of pituitary irradiation (yes/no) will be performed using the FAS. Following the ITT principle, patients are analyzed according to the drug and stratum they were assigned to at randomization.

If the 1-sided p-value is ≤ 0.025 , and the odds ratio (osilodrostat vs. Placebo) is > 1 , the null hypothesis will be rejected and the complete response rate in the osilodrostat arm will be considered higher than that in the placebo arm.

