2.5.4 Supportive analyses

As a supportive analysis to the primary analysis, an un-stratified Fisher's exact test of the primary endpoint will be performed using FAS.

In addition, both stratified CMH exact test and un-stratified Fisher's exact test of the primary endpoint will be performed using PPS.

To deal with potential missing mUFC at Week 12, multiple imputation assuming missing at random will be performed as a sensitivity analysis. For patients who discontinued the study early, mUFC collected during the follow-up visit at Week 12 will also be used for sensitivity analysis. If mUFC during the follow up visit is missing at Week 12, the patient will be considered as a non-responder.

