2.7 Analysis of secondary efficacy objectives

2.7.1 Assess the overall response rate at Week 12, Week 36, and Week 48

Proportion of complete responders (enrolled patients with $mUFC \leq ULN$), partial responders (enrolled patients with $mUFC > ULN$ and at least 50% reduction from baseline), and overall responders (enrolled patients with $mUFC \leq ULN$ or have at least 50% reduction in mUFC from baseline and $> ULN$) will be summarized using point estimates for every scheduled visit in the core and extension phase at which UFC is collected by treatment arm. Response rate will also be provided for all patients in the open-label period. 95% 2-sided CIs will be provided at Week 12, Week 36 and Week 48. To calculate the response rate during the open label treatment period, for the osilodrostat arm, the denominator will be the number of patients randomized to osilodrostat in Period 1; whereas for the placebo arm, the denominator will be the number of patients randomized to placebo in Period 1 who switched to osilodrostat. The FAS will be used for this analysis.

2.7.2 Assess the change in mUFC during the Core and Extension periods of the study

- Change in mUFC from baseline during the placebo-control period only

2.7.3 For the actual value and change in mUFC from baseline during placebo-control period, descriptive summaries will be provided. Compare the time-to-first control of mUFC during the placebo-controlled period between patients randomized to osilodrostat and placebo

Time-to-first control of mUFC is defined as the time (in days) from first study treatment date to the time of the first post-baseline mUFC collection that was $\leq ULN$ (based on central lab result) before discontinuation or completion of placebo-controlled period, whichever is earlier. It will be defined as censored at the last mUFC collection date if the mUFC was not controlled during the placebo-controlled period.

Time-to-first control of mUFC during the placebo control period will be analyzed using Kaplan-Meier plots and the logrank test. The quantiles of time-to-first control and corresponding two-sided 95% CI will be calculated using Kaplan-Meier methodology. FAS will be used for this analysis.

2.7.4 Assess the time-to-escape during treatment of osilodrostat up to Week 48

Escape is defined as the first loss of control of UFC that meets all of the following criteria:

- prior normalization of UFC has occurred ($mUFC \leq ULN$)

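### The log-rank test for time to first control leaves out the irradiation stratum that the randomisation and the primary test use

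*SAP*

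**What the plan says.** Protocol 6.5.2 stratifies the 2:1 randomisation by history of pituitary irradiation (yes/no), the only stratification factor. Core SAP 2.5.2 carries that factor into the primary analysis: a CMH "exact test stratified by the history of pituitary irradiation (yes/no) will be performed using the FAS".

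For time to first control, core SAP 2.7.3 says only that it "will be analyzed using Kaplan-Meier plots and the logrank test", using the FAS. Protocol 10.5.2.3 is the same in substance ("analyzed using Kaplan-Meier plots and the logrank test"). Neither mentions the stratum.

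Three other places in the core SAP bear on how to read this:

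- Section 2.1 mentions stratified analysis for one endpoint only: "To take stratification into account, the primary efficacy endpoint will be analyzed using Cochran-Mantel-Haenszel (CMH) exact test".
- Section 2.2.1 defines the FAS and adds that "patients will be analyzed according to the treatment and stratum they have been assigned to during the randomization".
- Section 2.5.4 labels its tests. It begins "As a supportive analysis to the primary analysis, an un-stratified" Fisher's exact test, and then lists stratified and unstratified tests on the per-protocol set.

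The final SAP (section 2.7.3) does not repeat the analysis and refers back to the interim CSR.

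**The concern.** The stated objective is to compare the randomised arms. Leaving aside the supportive tests of the primary endpoint, this log-rank test is the only named between-arm hypothesis test in Period 1 of the core SAP. It should follow the allocation scheme unless there is a reason for it not to.

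Stratified allocation keeps the irradiated share close to equal in the two arms, so stratum differences contribute little to the actual variation of the test statistic. The unstratified variance formula still counts that variation. If irradiation history is prognostic, the denominator is too large and the test rejects too rarely under the null. It can also lose power.

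There is a practical side too. The SAP labels its other tests as stratified or not, but gives this one no label. Two programmers could produce different p-values and both claim to have followed the plan.

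**Working it through.** **Inputs.** From core SAP section 3: 2:1 allocation, about 20% with prior irradiation, 60% versus 15% response, 42 + 21 evaluable patients, about 69 enrolled. From core SAP 1.1: 46 and 23 by arm. From the visit schedule: Days 15, 36, 57 and 85.

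**The plan's own figures.** No power is stated for the log-rank test, so the check on the inputs is the primary test.

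- Odds ratio: (0.60/0.40)/(0.15/0.85) = 8.5, as stated.
- Full enumeration of the one-sided 0.025 exact stratified CMH test at 42 versus 21 gives 92.2% to 92.4% over plausible stratum splits, against the stated 91%.
- Enrolment: 63 × 1.1 = 69.3, against about 69.

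The inputs reproduce closely enough to build on.

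**Stratum sizes.** 0.20 × 69 = 13.8, so 14 irradiated patients and 55 others. At 2:1 that is 9:5 and 37:18, which add to 46:23.

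**Test statistics.** At each event time u, let d be the events, n the number at risk, and d₁ and n₁ the same counts in the osilodrostat arm.

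- Unstratified: Z = Σ(d₁ − d·n₁/n) / √Σ[d·(n₁/n)(1 − n₁/n)(n − d)/(n − 1)].
- Stratified: form both sums within each stratum, add them over the two strata, then take the ratio.

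**Assumptions, none of them given in the documents.**

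- The irradiated versus non-irradiated hazard ratio (HR) for reaching control lies between 0.1 and 4.
- There is no drop-out.
- Events are recorded at the scheduled visits.
- Size is tested at a two-sided 5% level, because the SAP gives no level or sidedness for this test.

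**Results (%), unstratified / stratified.**

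| Stratum HR | Size, two-sided 5% | Power, 60% vs 15% | Power, 45% vs 15% |
|---|---|---|---|
| 0.1 | 3.6–3.9 / 4.6–5.0 | differs by under 0.5 | – |
| 0.25 | about 4.1 / 4.6–4.9 | 98.0 / 97.9 | 74.1 / 74.7 |
| 0.5 | 4.6 / 5.1 | 97.4 / 97.5 | 73.1 / 72.8 |
| 1 | 5.2 / 5.1 | 96.8 / 96.6 | 72.7 / 72.2 |
| 2 | 4.7 / 5.1 | 96.7 / 97.4 | 72.1 / 73.6 |
| 4 | 3.4 / 5.0 | 97.1 / 98.7 | 71.6 / 80.3 |

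Size for HR 0.5 to 4 comes from 40,000 trials per setting with 40% control in both arms. Its simulation error is √(0.05 × 0.95/40,000) = 0.11 points. The rows for HR 0.1 and 0.25 come from 20,000 trials (0.15 points), and their ranges reflect that size depends on the assumed null control rate. A smaller separate run of 4,000 trials (0.34 points) gave 4.4% / 5.0% at HR 0.25 and 4.1% / 5.2% at HR 0.1, in the same direction. Power comes from 2,000 trials per setting, with an error of about 0.4 points near 97% and 1 point near 72%.

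**One-sided size in favour of osilodrostat (nominal 2.5%, 40% control in both arms).** Unstratified / stratified: 2.0% / 1.9% at HR 1, 1.8% / 2.0% at HR 0.25 and 0.8% / 1.9% at HR 4. Both tests fall below 2.5% even with no stratum effect, so only the gap between them can be put down to the stratum.

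**The case against.** The strongest case against is that this is a preference with little consequence. An unstratified log-rank test is valid, and its error is in the safe direction. The endpoint is an other secondary one, outside the primary and key secondary sequence, and has no success rule or sample size of its own. The clear gaps need a strong stratum effect, for which the documents give no evidence. The 9-point power gap needs both HR 4 and a 45% response rate that is not the planning assumption. The irradiated stratum is sparse: about 5 placebo patients, so 5 × 0.15 = 0.75 expected events at the planned rate. The SAP already accepts unstratified tests of the Week 12 response as supportive, and time to first control is not the same response, because it counts control at any Period 1 visit. All of this stands, and it keeps the point minor.

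A second argument is that the text is only silent, and that the FAS sentence on assigned treatment and stratum might imply stratification. That does not settle it. The sentence says which assignment counts, not which test to run, and section 2.1 ties stratified analysis to the primary endpoint. If a stratified test was intended, section 2.7.3 still needs to say so.

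Finally, the final SAP says the result has already been reported. That limits what an edit can do now, but not whether the core SAP was complete.

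**Conclusion.** The point holds, at low importance. The log-rank test as written does not carry the stratum used in the randomisation and in the primary test, and nothing elsewhere in the documents supplies it or explains its absence. The result is a conservative test if irradiation history is prognostic, not a false-positive risk. Two-sided size falls from 5% to about 4% at a stratum HR of 0.25, and to about 3.4% at an HR of 4. At the planned effect the power cost is under 1 point for HRs from 0.1 to 2, and 98.65 − 97.05 = 1.6 points at HR 4. It reaches 80.3 − 71.6 = 8.7 points only with the smaller 45% versus 15% effect and HR 4. If irradiation has no effect on control, stratifying costs almost nothing (96.6% against 96.8%, within simulation error). These sizes rest on assumed stratum effects and no drop-out. The mismatch itself rests only on the text.

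**What to change.** In core SAP 2.7.3, specify a log-rank test stratified by history of pituitary irradiation (yes/no) as assigned at randomisation, and keep the unstratified log-rank test as supportive. This mirrors sections 2.5.2 and 2.5.4. Alternatively, state that the test is unstratified and why. The level and sidedness could be added in the same sentence.

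Since the final SAP places this result in the interim CSR, the practical step now is to state which version was run and report the other beside it, labelled as supportive and not as prespecified.

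The cost is a few words and one option in the survival procedure. No new data, sample size or multiplicity change is involved.

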7.1 Study flow and visit schedule

Table 7-1a, Table 7-1b and Table 7-2 list all of the assessments and indicate the visits at which they are performed with an “X” for the Core and Extension phases, respectively. Visit assessments window is ± 3 days, except for Day 1 which has a +3 day window.

All data obtained from these assessments must be supported in the patient’s source documentation. The table indicates which assessments produce data to be entered into the clinical database (D) or remain in source documents only (S) (“Category” column).

No eCRF will be used as a source document.

Table 7-3, Table 7-4, Table 7-5, Table 7-6, Table 7-7, [REDACTED] and Table 7-11 list all of the assessments required for the collection plan for Disease and Imaging Assessment, Clinical Laboratory parameters, Imaging, ECG, PK samples, Biomarkers samples, PPD [REDACTED] and Patient Reported Outcome, respectively.

Patients must end participation in the optional extension period within 4 weeks after Protocol Amendment 02 is approved at the site, or by Week 96, whichever occurs first.

Table 7-1a Visit evaluation schedule – Core – Period 1

	Category	Protocol Section	Screening			Core Treatment					Post-Treatment Follow-up				
			Wash-out	Post wash-out		Period 1					For patients discontinuing during Period 1				
Day			from -56	up to -15	-14 to -1	1	15	36	57	85	15	36	57	85	Last dose +30d
Week			from -8	up to -3	-2 to -1	1	2	5	8	12	2	5	8	12	
Obtain Informed consent	D	7.1.1	x												
IRT Contact	S		x			x	x	x	x	x				x	
IRT Randomization	S					x									
Patient history															
Demography	D	7.1.1.3	x												
Inclusion/Exclusion criteria	D	5.2 & 5.3			x										
Relevant medical history/Current medical conditions	D	7.1.1.3	x												
Cushing's Disease history	D	7.1.1.3	x												
Prior/concomitant medication	D	7.1.1.3				As required									
Physical examination	S	7.2.2.1	x			x	x	x	x	x	x	x	x	x	x
Body height	D	7.2.2.3	x												
Body weight and Waist Circumference	D	7.2.2.3	x			x	x	x	x	x	x	x	x	x	x
Physical features of Cushing's disease	D	7.2.1.2	x							x				x	
Signs and symptoms of adrenal insufficiency	D	7.2.2.1.1				x	x	x	x	x	x	x	x	x	x
Vital signs															
Body temperature/ Blood pressure/Pulse rate	D	7.2.2.2	x			x	x	x	x	x	x	x	x	x	x
Laboratory assessments															

	Category	Protocol Section	Screening			Core Treatment					Post-Treatment Follow-up				
			Wash-out	Post wash-out		Period 1					For patients discontinuing during Period 1				

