For cardiovascular and metabolic parameters associated with Cushing's disease (e.g. fasting glucose, HbA1c, fasting lipid profile, SBP, DBP, weight and waist circumference):

For actual and percentage change from baseline to Week 12, Week 36 and Week 48, descriptive summaries will be provided by treatment arm and for overall patients.

For the actual and percentage change from the baseline to the end or the last available measurement of the placebo control period, whichever occurs earlier, in addition to the descriptive summary, the mean difference between two randomized arm and associated 2-sided 95% C.I. will be estimated with adjustment for corresponding baseline parameter value. In addition, shift tables using normal/abnormal categories for BP (SBP, DBP), FPG, HbA1c, fasting lipid profile, weight and waist circumference from baseline at Week 12, 36, and 48 by randomized arms and for overall patients will be assessed. Normal for these parameters is defined as shown in [Appendix 3](#).

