10.8 Sample size calculation

Eligible patients will be stratified at randomization according to history of pituitary irradiation (yes/no). Based on the LCI699C2201 study, it is assumed that approximately 20% of randomized patients will have a history of pituitary radiation.

With 2:1 randomization ratio, to detect a difference of 45% in complete response rate between 60% in osilodrostat arm and 15% in placebo arm (equivalent odds ratio equals 8.5), a sample size of 42 patients in osilodrostat arm and 21 patients in placebo arm will provide 91% power based on a 1-sided CMH exact test at the 0.025 level. In order to adjust for drop-outs, an additional 10% patients will be enrolled. Thus a total of approximately 69 patients will be enrolled in the study.

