- patient reached highest tolerated dose of osilodrostat
- 2 consecutive mUFC (collected at scheduled visits) were above 1.3x ULN
- the loss of control of UFC is not related to a dose interruption or dose reduction due to safety reasons
- happens beyond Week 26 when the patients have a chance to be treated with doses as high as 30 mg bid

Time-to-escape is defined as the time (in weeks) from the first collection of post-baseline normal mUFC ($\leq ULN$) to the first mUFC $> 1.3 \times ULN$ on 2 consecutive scheduled visits on the highest tolerated dose of osilodrostat and not related to a dose interruption or dose reduction due to safety reasons after Week 26.

The highest tolerated dose is defined as

- 30 mg bid if reached, or
- being on a reduced dose due to safety reasonse such as AEs, or
- being on the same dose for at least 3 scheduled visits if the previous two criteria are not met.

For patients who attained normal mUFC ($\leq ULN$), time-to-escape will be analyzed using Kaplan-Meier plots. This will be performed by randomized treatment assignment and for the overall trial population using FAS. The quartiles of time to escape and corresponding two-sided 95% confidence interval will be calculated using Kaplan-Meier methodology. In addition, time-to-escape will be summarized using descriptive statistics for patients who escape. Time-to-escape will not be assessed for patients during the first 26 weeks.

Patients that have dose interruption or dose reduction for safety reasons will be censored at the time of the first dose interruption. Patients who discontinued the study are considered as censored. Patients who were controlled until the end of the study will be censored at the last mUFC collection date. FAS will be used for this analysis.

2.7.5 Assess the change from baseline in cardiovascular and metabolic related parameters associated with Cushing's disease during the core period of the study

For cardiovascular and metabolic parameters associated with Cushing's disease (e.g. fasting glucose, HbA1c, fasting lipid profile, SBP, DBP, weight and waist circumference):

For actual value and change from baseline to Week 12, Week 36 and Week 48, descriptive summaries will be provided by treatment arm and for overall patients in open-label period.

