For the actual value and change from the baseline to Week 12 or the last available measurement of the placebo control period, whichever occurs earlier, in addition to the descriptive summary, the mean difference between two randomized arms and associated 2-sided 95% C.I. will be estimated with adjustment for corresponding baseline parameter value. In addition, shift tables using normal/abnormal categories for BP (SBP, DBP), FPG, HbA1c, fasting lipid profile, weight and waist circumference from baseline to Week 12, 36, and 48 by randomized arms and for overall patients during the open-label period will be assessed. Normal for these parameters is shown in protocol Appendix 4. FAS will be used for this analysis.

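### The only between-arm cardiometabolic estimate lets an earlier Period 1 value stand in for a missing Week 12 value and omits the randomisation stratum, although repeated measures are scheduled

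*SAP*

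**What the plan says.** Core SAP (01-Apr-2019) 2.7.5 plans three outputs for the cardiovascular and metabolic parameters.

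- At Weeks 12, 36 and 48, "descriptive summaries will be provided by treatment arm and for overall patients in open-label period".
- Shift tables between normal and abnormal categories.
- One between-arm estimate: the mean difference in change from baseline to Week 12 "or the last available measurement of the placebo control period, whichever occurs earlier". This difference, with its two-sided 95% CI, "will be estimated with adjustment for corresponding baseline parameter value".

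Protocol 10.5.2.5 has the same last-value rule and the same single covariate: "the mean difference between two randomized arm and associated 2-sided 95% C.I. will be estimated with adjustment for corresponding baseline parameter value". The final SAP (01-Dec-2020) 2.7.5 adds only further visits.

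On the stratum, SAP 2.1 says: "The randomization will be stratified by history of pituitary irradiation". It then names one use: "To take stratification into account, the primary efficacy endpoint will be analyzed using Cochran-Mantel-Haenszel (CMH) exact test".

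Protocol Table 7-1a schedules "Body weight and Waist Circumference" and blood pressure at Day 1 and Weeks 2, 5, 8 and 12. After Day 1, fasting glucose, lipids and HbA1c are scheduled in Period 1 at Weeks 8 and 12 only. The same weeks are scheduled for patients who stop drug in Period 1.

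**The concern.** The rule is last observation carried forward in effect, though neither document uses that name. Under Protocol 4.1 and 6.2.1, dose decisions follow the Week 2, 5 and 8 results, so a dose set after Week 8 is first reflected at Week 12. A Week 2, 5 or 8 value therefore belongs to a different stage of titration. Placing it in a Week 12 analysis mixes time points, and the CI treats it as if it had been measured at Week 12. No informative dropout is needed for this to bias the Week 12 difference. It is enough that the between-arm difference changes over Period 1.

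This estimate is the trial's only between-arm estimate with a CI for these parameters. Unlike the primary endpoint (SAP 2.5.4), it has no missing-data sensitivity analysis.

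It is also unclear which value is the last available one. SAP 2.1.1 gives Period 1 follow-up values a sensitivity role for efficacy. SAP Table 2-1, however, labels the follow-up visits after stopping drug (301–304) as part of the double-blind period. On one reading, an earlier on-drug value replaces a Week 12 value that was actually measured. On the other, the off-drug Week 12 value is used.

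**Working it through.** **Plan figures.** The documents give no SD, effect size or power for this contrast, so there is no plan figure to reproduce for it. The 91% power in Protocol 10.8 concerns the primary endpoint. Enumerating the exact stratified test with strata of 34/17 and 8/4 gives 92.2%, and this point does not change it.

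**Inputs from the documents.** Period 1 visit weeks (Table 7-1a); planned arms of 46 and 23 (SAP 1.1); a 10% dropout allowance (Protocol 10.8); a stratum in which "approximately 20% of randomized patients will have a history of pituitary radiation", about 0.20 × 69 ≈ 14 patients.

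**Assumptions.** The active-arm effect grows linearly to Week 12, placebo stays flat, and dropout is unrelated to outcome. With a flat placebo arm, only active-arm dropout d matters. If placebo drifts, placebo dropout matters too.

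**Step 1: simple attenuation.** If f is the fraction of the Week 12 effect present at the last value, the rule recovers (1 − d) + d·f.

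For blood pressure, weight and waist with last values at Weeks 5 and 8 equally often, f = (5/12 + 8/12)/2 = 0.542.

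- d = 10%: 0.90 + 0.10 × 0.542 = 0.954.
- d = 20%: 0.80 + 0.20 × 0.542 = 0.908.

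**Step 2: dropout times spread evenly over 0–12 weeks.** Patients with no post-baseline value leave the analysis.

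- Visits at Weeks 2, 5, 8 and 12: the last value is Week 2, 5 or 8 with probability 3/12, 3/12 and 4/12. The carried sum is (3/12)(2/12) + (3/12)(5/12) + (4/12)(8/12) = 0.368. At d = 10%: (0.90 + 0.10 × 0.368)/(0.90 + 0.10 × 10/12) = 0.953. At d = 30%: (0.70 + 0.30 × 0.368)/(0.70 + 0.30 × 10/12) = 0.853.
- Visits at Weeks 8 and 12: only Week 8 can be carried. At d = 10%: (0.90 + 0.10 × (4/12)(8/12))/(0.90 + 0.10 × 4/12) = 0.988. At d = 30%: 0.7667/0.80 = 0.958.

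**Step 3: simulation.** Settings: 46 versus 23 patients, 600 runs, a true Week 12 effect of −0.8 SD, correlation 0.6 per 4 weeks and dropout times as in Step 2. The repeated-measures model has visit, arm-by-visit and baseline-by-visit terms, with its covariance taken as known.

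| Parameters | Dropout, active/placebo | Last value, % of true | Repeated measures, % of true | SE ratio, repeated measures to last value |
|---|---|---|---|---|
| BP, weight, waist | 10%/10% | 94 | 98 | 0.261/0.251 = 1.04 |
| | 30%/10% | 86 | 101 | 0.277/0.255 = 1.09 |
| | 10%/50% | 97 | 101 | 0.313/0.244 = 1.28 |
| | 30%/30% | 85 | 99 | 0.290/0.249 = 1.16 |
| Glucose, lipids, HbA1c | 10%/10% | 98 | 99 | 0.255/0.249 = 1.02 |
| | 30%/10% | 96 | 100 | 0.286/0.279 = 1.03 |
| | 10%/50% | 99 | 100 | 0.314/0.287 = 1.09 |
| | 30%/30% | 96 | 100 | 0.285/0.269 = 1.06 |

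Monte Carlo error is about 0.25/√600 = 0.010, or 1.3 points on this percentage scale. The results agree with Step 2, and the gap between 94% and 97% at 10% active-arm dropout is within that noise.

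The 96–99% for glucose, lipids and HbA1c depends on patients who stop before Week 8 leaving the analysis. If every active-arm dropout had a Week 8 value (f = 0.67), recovery would be about 97% at d = 10% and 93% at d = 20%.

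**Step 4: stratum.** If the stratum explains a share r² of residual variance, the SE ratio is √((1 − r²) × 66/65). This is 1.003, 0.982 and 0.956 for r² = 1%, 5% and 10%.

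**The case against.** The protocol and SAP agree, the rule was prespecified, and the estimate is an other-secondary CI with no decision rule, outside the sequential test. All of that stands. This is a weakness of method, not an inconsistency.

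A reader might infer that the rule must bias towards no effect and so understates benefit. The documents do not support that. Protocol 1.2.1.2.3 and 2.6 say the drug itself may raise blood pressure and weight through precursor accumulation, so even the sign of those differences is uncertain. Protocol 6.1.3 calls for rescue treatment of co-morbidities during Weeks 1–12, with a lower suggested glucose threshold after Week 6. More rescue in the placebo arm could shrink the Week 12 difference, and an earlier value would then overstate it.

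Carry-forward may also be rare. Protocol 7.1.6 requires follow-up visits through Week 12 after early stopping, and by-arm Week 12 summaries are reported as well.

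The remedy is not free. At 10%/10% dropout for blood pressure, weight and waist, root mean squared error is √(0.052² + 0.251²) = 0.256 for the last-value rule and √(0.014² + 0.261²) = 0.261 for repeated measures. The gain is a clear Week 12 target and an interval that reflects the missing values, not a smaller total error. For glucose, lipids and HbA1c, with one intermediate visit, the gain is slight. Including off-drug values, possibly on other cortisol-lowering therapy (Protocol 7.1.4), changes the estimand and needs an explicit choice.

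Omitting the stratum mainly affects precision and consistency with the design. It is not evidence of a biased comparison.

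**Conclusion.** The point holds as a low-cost improvement. The estimate does not target the Week 12 difference if that difference changes during titration, and this is so even under missing at random. Its direction depends on the time course and on rescue treatment.

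The size is small at the planned 10% dropout: about 5% attenuation for blood pressure, weight and waist, and 1–3% for glucose, lipids and HbA1c. At 30% active-arm dropout it reaches about 15% for the first group. These figures assume linear growth, a flat placebo arm and dropout unrelated to outcome, none of which the documents establish.

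The undefined status of values measured after stopping drug needs resolving whatever the size. Nothing here touches the primary or key secondary conclusions. The core SAP's document history records removal of longitudinal models for mUFC and patient-reported outcomes. It should not be read as showing that such a model was ever planned for these parameters.

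**What to change.** In Core SAP 2.7.5:

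1. Make the main between-arm analysis a repeated-measures model on the scheduled Period 1 values: blood pressure, weight and waist at Weeks 2, 5, 8 and 12; glucose, HbA1c and lipids at Weeks 8 and 12. Include arm, visit, arm-by-visit, baseline-by-visit and the irradiation stratum. Report the Week 12 difference with its 95% CI.
2. Keep the last-value ANCOVA, with the stratum added, as a sensitivity analysis.
3. State whether values from follow-up visits 301–304 are included in the main analysis, and report the result both with and without them.

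The final SAP says the core analysis has already been reported. If the model is run now, label it supplementary.

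The cost is SAP wording, slightly more programming than ANCOVA and a somewhat wider CI. No new data are needed, and adding the stratum to the existing ANCOVA costs almost nothing.
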